stimulation (cTBS) did not find group-level clinically meaningful change, although an extended dose (total of 6 weeks daily) did improve outcomes with 1Hz.³⁶ Importantly, in the only study measuring neural correlates of treatment, Wu et al.³³ detected significant decreases in activation of SMA and functionally connected CSTC nodes (i.e., bilateral M1) after only a 2 day course of cTBS, leading to continued interest in using TMS to alter tic-related neural pathology.

Our recent research suggests rTMS improves tic suppression ability more robustly than it reduces baseline tic frequencies. PI [name] measured acute effects of 1 Hz vs. sham rTMS over SMA using the TST (K23MH103617; for detail see "Preliminary Data" below) and found that active 1Hz rTMS enhances tic suppression ability. Notably, reduction in tic frequency was more robust in conditions measuring tic suppression ability compared to a "free to tic" baseline. These data suggest that inhibitory stimulation of SMA with rTMS may benefit those with tics by enhancing their capacity to voluntarily inhibit tics.

2.3. Existing Literature: Taken together, the existing literature and our preliminary data suggest that augmenting CBIT with inhibitory stimulation of SMA using TMS may boost tic suppression ability, which in turn may increase the efficacy of CBIT. This synergistic approach aligns with converging evidence suggesting that combining brain stimulation with targeted therapy is a potentially powerful approach for treating neuropsychiatric disorders.³⁷

3. Study Endpoints/Events/Outcomes

- 3.1. Primary Endpoint/Event/Outcome:
 - 1) Neural target engagement: Within-subject change in resting state fMRI connectivity of SMA-mediated brain circuits.
 - 2) Behavioral target engagement: Within subject change in tic suppression ability as measured by the Tic Suppression Task (TST).
- 3.2. Secondary Endpoint(s)/Event(s)/Outcome(s):
 - 1) Two TMS procedures, both intended to inhibit activity in SMA, will be compared using data from our safety and feasibility measures.
 - 2) Between group differences on secondary measures of clinical and neural function.

4. Study Intervention(s)/Investigational Agent(s)

4.1. Description: All participants will receive 10 daily sessions of CBIT, a wellestablished behavioral treatment that is considered by the American

PROTOCOL TITLE: Transcranial Magnetic Stimulation to Augment Behavior Therapy for Tics VERSION DATE: 2/24/2022

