- Motor threshold (MT) determination. Resting MT will be defined as the minimum magnetic flux needed to elicit a threshold EMG response (≥50 mV in peak-to-peak amplitude) in a resting target muscle (abductor pollicis brevis) in 5/10 trials using single-pulse TMS administered to the contralateral hand area of primary motor cortex. The MT procedure will occur during the first CBIT+TMS visit and this MT will be used to calculate stimulation intensity for all TMS sessions. Stimulation intensity may be adjusted to improve tolerability; all such adjustments will be reviewed by a study physician and documented.
- rTMS coil positioning: Individualized using fMRI and electric field modeling. TMS effects strongly depend on the spatial distribution of the induced electric field in the brain.⁶⁴ TMS targeting will be based on individual-level identification of the optimized coil location and orientation that induces the strongest electric field within SMA that show the highest parametric fMRI activation during the bilateral finger tapping task. This approach accounts for individual differences in physiology, which are prominent in developmental samples. We will create individual finite element method (FEM) models for each participant using the computer program SimNIBS (Danish Research Center for Magnetic Resonance, Copenhagen, Denmark and the Technical University of Denmark (Kgs Lyngby, Denmark) and participant anatomical MRIs, following procedures established by Co-I [name].65-67 Coil placement. The coil placement and orientation will be based on the individual models and continually monitored using a stereotaxic neuronavigation system (BrainSight 2.3.5, Rogue Research, Montreal, Quebec, Canada) running on an Intel-based Macintosh computer (Apple, Inc, Cupertino, CA). This

PROTOCOL TITLE: Transcranial Magnetic Stimulation to Augment Behavior Therapy for Tics VERSION DATE: 2/24/2022

system permits targeting of individual cortical locations using individual structural and functional MRI.

- TMS administration. TMS parameters are as follows:
 - Pulse frequency: 1 Hz, cTBS, or sham (randomized between subjects)
 - Pulse sequence:
 - 1 Hz: single train of 2000 pulses at 110% resting motor threshold (33 min duration)
 - cTBS: bursts of 3 pulses at 30 Hz repeated every 200ms (5 Hz burst frequency), single uninterrupted 40 sec train, 600 total pulses at 90% resting motor threshold (40 sec duration)

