 - Sham: to enhance blinding, half of sham participants will be exposed to the 1 Hz sequence and half will be exposed to the cTBS sequence
 - Number of sessions: 10 day sessions, delivered daily on weekdays
 - Immediately after the stimulation ends, the participant will be transitioned to a private room for the CBIT session. The *TMS Adverse Effects Questionnaire³⁹* will be completed by the participant and TMS operator at the end of each study visit.
 - rTMS sessions will be video recorded to later be coded for tic occurrences.
- Blinding procedures will be implemented to control for expectancy effects related to TMS stimulation. Persons who will be blind to TMS status are: participants; parents (if applicable); study staff administering clinical assessments, coding TST videos, delivering CBIT therapy, and collecting the MRI data; and all study investigators except Drs. [name] and [name]. Unblinded personnel will be [name], the study statistician and person responsible for randomization scheme oversight; [name], TMS operator supervisor; and the TMS operator. Staff who administer clinical rating scales and code TST videos will not be present for a given participant's CBIT+TMS visits to also ensure blinding to overall therapy progress. Staff will be trained and supervised on assessment scales by [name], who will audit YGTSS administrations for inter-rater reliability. Staff will be trained in TST coding by [name], who will code a set of video clips to monitor inter-rater reliability. For each of these measures (YGTSS

PROTOCOL TITLE: Transcranial Magnetic Stimulation to Augment Behavior Therapy for Tics VERSION DATE: 2/24/2022

and TST), the supervisor will audit 100% of the first ¹/₃ of the initial visits, 50% of the second ¹/₃ of participants, and 20% of the third ¹/₃ of the participants for inter-rater reliability. Forms assessing blinding adequacy will be given to participants, parents, and blinded staff who conduct CBIT sessions and assessments visits at post-treatment.

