• **TMS**, general: Noninvasive brain stimulation techniques (NIBS) have been used with thousands of children and adults. Three major review papers have specifically addressed the safety of TMS, rTMS, and transcranial direct current stimulation (tDCS) in pediatric populations.^{76,139,140} Collectively, these papers indicate that NIBS has been used in healthy children and the following pediatric clinical conditions: tic disorders/Tourette Syndrome, stroke, attention deficit hyperactivity disorder (ADHD), major depressive disorder, autism spectrum disorders (ASD), multiple sclerosis, epilepsy and seizure disorders, malnourishment, Rett Syndrome, Cockayne's Syndrome, spasticity, schizophrenia/auditory hallucinations, language disorders, and dystonia. TMS is used as both a testing tool and a treatment. As a testing tool, the majority of children tolerate TMS well: in one study, 85% of the sample (n = 34 children) said they would do TMS again, and they ranked TMS as being more enjoyable than going on a long car ride, going to the dentist, or getting a shot at the doctor's.¹⁴¹ No person experienced any change in their neurological examination, hearing, or any other tests that were performed, and all symptoms disappeared by the next day. Risks associated with rTMS are rare but should be recognized and prevented with appropriate precautions. Serious adverse risks include the induction of a seizure. Mild adverse effects include fainting, headache, dental pain, nausea, and other changes in memory, mood, and hearing. The overall occurrence of a mild adverse event is 5% in sham and real rTMS sessions combined.142 rTMS delivery may also interfere with implanted devices. rTMS is not appropriate for persons with medical devices such as deep brain stimulators, pacemakers and medication pumps.

Participants will undergo thorough screening to determine individual eligibility for TMS. Very extensive exclusion criteria are applied for participation in this study to ensure that enrolled

PROTOCOL TITLE: Transcranial Magnetic Stimulation to Augment Behavior Therapy for Tics VERSION DATE: 2/24/2022

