participants are not at any excess risk for medical adverse events. The only absolute *contraindication* to TMS is the presence of metal hardware in close contact with the discharging coil. Certain medications may increase the risk of seizure with TMS. Potential participants will be assessed for use of such medications. Individuals will be excluded from participation in the event they are currently taking any agents in this group. In addition, medical records reviewed by a study physician (Drs. [name] or [name]) and completion of the Screening Questionnaire for TMS Candidates, developed by the Safety of TMS Consensus Group⁶⁹ will be administered and reviewed for TMS eligibility. An appropriately trained staff member will administer TMS and be present throughout TMS sessions to observe the participants. A standard questionnaire assessing side effects specific to TMS (TMS Adverse Effects Questionnaire³⁹) will be completed at every TMS visit to identify and address any treatment-emergent adverse effects. The staff member delivering TMS will have updated first responder training, CPR training, and training in seizure management. The TMS administrator will immediately call 911 if serious adverse events occur.

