the stimulation groups, and baseline x group interactions. Random effects will be used to model within-subject variation from the first-level analyses. Altogether, the LME will allow us to model how the within-subject change in activation from pre-treatment to post-treatment differs across active and sham conditions. *In addition*, we will also investigate the effects of each TMS regimen on the connectivity in the entire CSTC. To this end, we will extract the ROI-level time courses from each region in the CSTC, and we will use partial correlations to obtain an estimate of connectivity between each ROI pair within the CSTC while accounting for the data observed in the other ROIs. Given the collection of partial correlations for each study participant, we will use the SPU test, which uses the collection of partial correlations simultaneously, to assess for group differences across the sham and TMS regimens.⁷⁵

- Aim 2. Target engagement: Behavior. Hypothesis: Either or both active TMS groups will show within-subject improvement (small effect size of at least Cohen's d = 0.3) in tic suppression ability as measured by the Tic Suppression Task (TST). TST "tic suppression ability" scores will serve as the primary outcome in an ANOVA model. An ANOVA will be used to establish if there exist differences in how the 1Hz, cTBS, and sham conditions affect change in tic suppression ability from pre- to post-treatment. Group indicators for these conditions will be the primary predictors for the model.
- Aim 3. Assess dose-response relationship. Changes in brain (Aim 1) and behavior (Aim 2) targets will be compared between active TMS groups (1Hz rTMS vs. cTBS) using ANOVA. In the case that both active TMS regimens are found superior to sham, we will compare the regimens on safety and feasibility. We will use 2-sample t-tests to compare the two regimens using data from our safety and feasibility measures and prioritize the regimen with significantly better (p<.05) outcomes.
- 15.2. Power Analysis: In Aim 1, hypothesis 1 our proposed sample size after accounting for expected attrition will give us 80% power to detect an effect size of at least $\eta^2=0.18$ for differences in SMA activation between active TMS and sham. For Aim 2, our proposed sample size will give us 80% power to detect an effect size of at least d = 0.90 for a within-subject improvement in tic suppression ability. Our preliminary data showed effect sizes of this magnitude.

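### The planned safety comparison is 1 Hz against cTBS only, conditional on efficacy in 15.1 but not in 3.2, and neither section uses the sham arm

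*Combined protocol and SAP*

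**What the plan says.** Section 15.1, Aim 3, first sets a condition: "In the case that both active TMS regimens are found superior to sham, we will compare the regimens on safety and feasibility". It then gives the method: "We will use 2-sample t-tests to compare the two regimens using data from our safety and feasibility measures". The regimen with significantly better results at p<.05 is to be prioritised. The opening sentence of Aim 3 makes clear that the regimens are the two active groups.

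Section 3.2, item 1, lists the comparison as a secondary endpoint without any condition: "Two TMS procedures, both intended to inhibit activity in SMA, will be compared using data from our safety and feasibility measures". Item 2 of 3.2 covers between-group differences in clinical and neural function and does not mention side effects.

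Data collection is not restricted by arm. Under TMS administration in section 5.2, the TMS Adverse Effects Questionnaire "will be completed by the participant and TMS operator at the end of each study visit". Section 13.1 repeats that it "will be completed at every TMS visit to identify and address any treatment-emergent adverse effects". For sham, section 5.2 says that "half of sham participants will be exposed to the 1 Hz sequence and half will be exposed to the cTBS sequence".

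**The concern.** A trial with a randomised sham arm can separate what stimulation adds from what participants would report anyway: headache after a long visit, scalp discomfort from the coil, nausea, tiredness. The plan collects the data for this, but the safety analysis it describes never uses the sham group.

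Two consequences follow. First, a side effect that both active regimens cause about equally cancels out of 1 Hz versus cTBS. Second, under 15.1 the comparison is not run at all unless both regimens beat sham. A regimen with side effects and no demonstrated benefit is a case where readers most need the safety result. The hypotheses in Aims 1 and 2 are worded so that one active group may succeed without the other, so the plan itself foresees outcomes in which the condition fails.

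At stake is the quality of safety reporting in a sample that starts at age 12. The primary and efficacy analyses are unaffected.

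**Working it through.** The plan gives no sample size, power or precision figure for any safety comparison, so there is none to reproduce. The check is first textual, then illustrative.

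**1. Where sham is used.**

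| Place | Contrast | Condition | Sham used for side effects? |
|---|---|---|---|
| 3.2 item 1 | 1 Hz vs cTBS, safety and feasibility | none | no |
| 3.2 item 2 | between groups, clinical and neural function | none | side effects not named |
| 15.1 Aims 1 and 2 | active vs sham, brain and tic suppression | none | no |
| 15.1 Aim 3 | 1 Hz vs cTBS, safety and feasibility | both superior to sham | no |
| 13.1 adverse events | case-by-case relatedness rating | none | no contrast |
| 18.2 DSMB | adverse event review, annual key-event report | none | no contrast stated |

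If 15.1 is followed and either regimen fails to beat sham, the endpoint in 3.2 item 1 has no analysis.

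**2. Inputs for the illustration.** Total n = 60 and three arms (section 5.1). The allocation ratio is not stated, so 20 per arm without attrition is an assumption. The event counts are also assumptions. The only rate in the documents is in section 13.1: "The overall occurrence of a mild adverse event is 5% in sham and real rTMS sessions combined". It combines sham and real stimulation, so it cannot isolate an effect of stimulation. Its unit is also unclear: read per participant it is 5%; read per session, with 10 independent sessions, it is 1 - 0.95^10 = 40%.

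**3. Formula.** Newcombe's score interval for p1 - p2, where l and u are the Wilson limits of each proportion:

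- lower = (p1 - p2) - sqrt[(p1 - l1)^2 + (u2 - p2)^2]
- upper = (p1 - p2) + sqrt[(u1 - p1)^2 + (p2 - l2)^2]

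Example, 6/40 versus 1/20. The Wilson limits are 0.0706 to 0.2907 and 0.0089 to 0.2361.

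- lower = 0.10 - sqrt(0.0794^2 + 0.1861^2) = 0.10 - 0.202 = -0.102
- upper = 0.10 + sqrt(0.1407^2 + 0.0411^2) = 0.10 + 0.147 = 0.247

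**4. Cancellation.** Suppose 10/20 are affected in each active arm and 3/20 on sham.

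- 1 Hz versus cTBS (the planned contrast), 10/20 vs 10/20: 0 points (-28 to 28)
- One active arm versus sham, 10/20 vs 3/20: 35 points (6 to 57)
- Pooled active versus sham, 20/40 vs 3/20: 35 points (9 to 53)

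**5. Precision of the added estimate.**

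- 3/20 vs 1/20 (one arm): 10 points (-11 to 31)
- 6/40 vs 1/20 (pooled): 10 points (-10 to 25)
- 10/40 vs 1/20: 20 points (-2 to 36)
- 11/40 vs 1/20: 22.5 points (0.7 to 38)
- 24/40 vs 8/20 (40% background): 20 points (-6 to 43)

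**6. Mixed sham.** Sessions last 33 min with the 1 Hz sequence and 40 sec with cTBS. Suppose sham rates are 25% and 5% respectively, and stimulation adds 20 points to each. The active rates are then 45% and 25%, and an evenly split sham arm averages (25 + 5)/2 = 15%. Against all sham, 1 Hz shows 45 - 15 = 30 points and cTBS 25 - 15 = 10. Pooled active, averaging 35%, shows 35 - 15 = 20. The per-arm figures partly reflect the sequence mix in sham. A sequence-matched sham group has about 10 people: 10/20 vs 2/10 is 30 points (-7 to 55).

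**The case against.** The strongest reply is that the planned contrast does its stated job. Aim 3 is about dose-response and picking a regimen, and sham cannot help choose between two active procedures. That stands, and the contrast should stay.

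A second reply is that safety is handled elsewhere. Side effects are recorded at every TMS visit, events are logged and rated for relatedness, and a DSMB reviews adverse event data with an annual key-event report from the study statistician, who is unblinded. This also stands. A reader might infer that participants are unprotected or that no by-arm table will ever exist. The documents do not support either inference: monitoring is in place, and the DSMB charter, which is mentioned but was not supplied, may call for by-arm tables. A monitoring table would still not be an estimate specified in the analysis plan.

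Third, 3.2 is a short endpoint list and 15.1 supplies the detail, so the missing condition may be abbreviation and not contradiction. That is fair as to intent. The practical effect remains: a listed secondary endpoint may go unanalysed.

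Fourth, a reader might infer that the 15.1 population, which needs at least one completed CBIT session, loses everyone who stops TMS early. It does not. It loses only those who complete no CBIT session at all; someone who stops stimulation but attends that day's CBIT is kept.

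Finally, pooling is debatable, because 2000 pulses at 110% of threshold and 600 at 90% are different exposures. That is a reason to show each arm against sham beside the pooled figure.

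**Conclusion.** The point holds as a gap in the planned analysis. Sections 3.2 and 15.1 specify no side-effect estimate against sham, and 15.1 makes the only between-arm safety comparison depend on efficacy in both active arms. It is worth considering and cheap to fix, and it changes no primary or efficacy inference.

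Its size can only be illustrated. With an assumed 20 per arm, a 35-point excess common to both regimens would appear as 0 in the planned contrast. The sham comparison would be imprecise, with a 95% interval of about -10 to 25 points around a 10-point pooled difference. The textual finding does not depend on these assumed rates. How often the 15.1 condition would be met cannot be said, because Aim 3 does not define superiority.

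**What to change.** In 3.2 item 1 and 15.1 Aim 3:

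- Report side effects by arm (1 Hz, cTBS, sham) whatever the efficacy result, among everyone who received any TMS session. Use the TMS Adverse Effects Questionnaire and the adverse event form; a suitable summary is the proportion with at least one treatment-emergent effect.
- Give risk differences with score or exact 95% CIs for each active arm versus sham and for pooled active versus sham, labelled as estimates and not tests.
- State that sham mixes the two sequences, and show the sham counts by sequence. Note also that the TMS operator, who helps complete the questionnaire, is unblinded.
- Keep 1 Hz versus cTBS for choosing the regimen, and make the two sections agree on when it is run.

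The cost is wording in two sections and one table from forms already in use. The downside is wide intervals that will often be unable to rule out no difference.

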20.2. Contract Language: N/A

21. Consent Process

Consent Process (when consent will be obtained): Child assent and informed consent from the parent (to allow their child to participate in this study) or adult consent only (for participants aged 18 years or older) will be administered at the start of the pre-treatment assessment visit and will be required for participation in study procedures. Specifically, the consent and youth assent documents will be read through with all potential participants, and focus will be placed on potential risks and benefits associated with study participation, any alternatives to participating in the research, that opportunities to receive treatment will not depend upon research participation, clinical care will not be affected by study participation, and that participation is voluntary. In addition, the investigators will try to foster an open exchange of information, encouraging potential participants and their families to discuss study particulars and ask questions prior to research involvement; to receive a copy of the consent form to discuss with family and friends, if desired; and to continue asking any questions that might arise during participation. Parents/adult participants will be informed that all assessment information will be kept confidential with the following three exceptions explicitly stated: participant or parent (1) suicidality, (2) homicidality, and (3) abuse. Finally, details on written consent and child assent forms will be presented in simple language approved by UMN IRB. Among individuals who provide informed consent, only those who fully meet the study entry criteria after the pretreatment assessment will be allowed to continue with the rest of the study. Participants who are active in the study when they turn 18 will be re-consented at the next visit/ session before additional study activities begin.

Potential participants will meet with the designated team member for assent/consent and potential enrollment. Consenting to research activities will take place in a private room at the Study Site or electronic consent may be conducted remotely, by phone or videocall. Participants over 18 years of age will need to meet via videocall or in-person for the administration of the MacCat-CR. These participants will not complete this procedure via phone call per institutional policies. During this visit, the qualified Site Study personnel authorized by the Site Principal Investigator and the potential participant and their parent/ legal guardian will discuss the nature of the trial, the purpose of the research, the trial procedures, the possible risks and benefits of participation, confidentiality and the voluntary nature of participation in the trial (emphasizing the participant's right to withdraw from the study at any time).

PROTOCOL TITLE: Transcranial Magnetic Stimulation to Augment Behavior Therapy for Tics VERSION DATE: 2/24/2022

Following this discussion, potential participants and their parents/legal guardians will be offered the opportunity and encouraged to ask any study-related questions and enroll by providing written assent/consent on the IRB-approved form. For remote consent discussions, participants and/or their parent/legal guardian will navigate to the electronic consent/assent form shared through REDCap. The electronic consent/assent form has been designed so that the participant and their parent/legal guardian are unable to complete the consenting process without completing the consenting process with a member of the research team. Participants and/or their parent/legal guardian will first receive a "Read Only" version of the consent prior to the consent visit. Only after the research coordinator has completed the informed consent discussion and determined the parent/legal guardian and/or participant fully understand all procedures and are capable of informed consent will he/she sign the electronic consent form and deliver an "editable" version of the electronic consent form which the participants and/or their parent/legal guardian will be able to sign. For the electronic consent process to be considered complete, the consenting team member will access REDCap in real-time to confirm the parent/legal guardian and/or participant have signed the consent/assent form correctly.

Participants will be allowed as much time as needed, with Site Study personnel or in private, to review consenting documents before making the decision to participate. Potential participants may invite a friend or family member to be present during the visit, to further discuss their decision to enroll and/or contact (e.g., phone call) a friend or family member that is not physically present for discussion before deciding to enroll. At the potential participant's request, Site Study personnel may be asked to 'step-out' of the room or end/mute the call during remote discussions, to provide privacy for such discussions. In addition, potential participants will be provided the option to defer their decision to allow them to review the consent form and other study information forms at their convenience, and later reconnect with the Site Study team remotely or return to the Study Site to enroll (i.e., complete the informed consent procedures). No study activities will take place prior to completion of the consenting process.

21.1. Waiver or Alteration of Consent Process (when consent will not be obtained): N/A

- 21.2. Waiver of Written/Signed Documentation of Consent (when written/signed consent will not be obtained): N/A
- 21.3. Non-English Speaking Participants: N/A

PROTOCOL TITLE: Transcranial Magnetic Stimulation to Augment Behavior Therapy for Tics VERSION DATE: 2/24/2022

- *21.4.* Participants Who Are Not Yet Adults (infants, children, teenagers under 18 years of age):
 - Individuals under the age of 18 years will be considered to not have attained the legal age for consent to participate in research. Participants who are active in the study when they turn 18 will be reconsented at the soonest possible time before additional study activities are completed.
 - Parental permission will be obtained from one parent, even if the other parent is alive, known, competent, reasonably available, and shares legal responsibility for the care and custody of the child.
 - Legal guardians will be allowed to provide permission if they provide documentation of their status as a legal guardian.
 - Assent will be obtained from all of the children.
 - The attached "Assent Form" will be used to document child assent prior to starting any study activities.
- 21.5. Cognitively Impaired Adults, or adults with fluctuating or diminished capacity to consent: N/A

